7.2.1. Summaries of Numeric Laboratory Results

Descriptive statistics (sample size, mean, standard deviation, median, Q1, Q3, minimum and maximum) will be provided by monitoring group for each laboratory test specified in the study protocol as follows:

- Baseline values
- Values at each post-baseline analysis window
- Change from baseline at each post-baseline analysis window

In the case of multiple values in an analysis window, data will be selected for analysis as described in Section 3.8.3 *Selection of Data in the Event of Multiple Records in a Window*. Laboratory data collected prior to the first dose date of TDF will be included in data listings.

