Baseline measures for Groups 1 and 2 will include laboratory assessments for HBV DNA, HBV serology, HCV, HDV, and HIV polymerase chain reaction (PCR) testing, HBV genotyping, serum renal and bone chemistries, liver function, hematology, urinalysis. Dual Energy X-ray Absorptiometry (DEXA) imaging and a physical exam, including current concomitant medications (including dietary supplements) and any renal or bone AEs, will also be collected.

FREQUENCY OF STUDY PROCEDURES ([Appendix 2](#)):

Subjects enrolled to either Group 1 or 2 will have the following measures assessed:

- HBV DNA: every 12 weeks from Baseline to Week 96
- HBV serology: every 24 weeks from Baseline to Week 96
- Liver chemistry (i.e., alanine aminotransferase (ALT), alkaline phosphatase (ALP), aspartate aminotransferase (AST), total and direct bilirubin, total protein, albumin, gamma glutamyl transpeptidase (GGT), lactate dehydrogenase (LDH), creatine kinase (CK): every 24 weeks from Baseline to Week 96
- Hematology (i.e., complete blood count with differential and platelets, PT/INR): every 24 weeks from Baseline to Week 96
- Physical Examination and Drug Dispensing: every 12 weeks from Baseline to Week 96

Subjects enrolled to Group 1 will have the following additional monitoring:

- DEXA: every 24 weeks from Baseline to Week 96 (5 scans)
- Serum bone chemistry (i.e., calcium, phosphorus, vitamin D levels (25-hydroxy and 1,25 dihydroxyvitamin), parathyroid hormone (PTH), osteocalcin, bone-specific alkaline phosphatase, N and C telopeptides): every 24 weeks from Baseline to Week 96
- Serum renal chemistry (i.e., glucose, creatinine, calculated creatinine clearance, magnesium, bicarbonate, chloride, potassium, sodium): at 4 weeks and 12 weeks from Baseline and every 12 weeks thereafter to Week 96, according to SmPC

- Urinalysis (i.e., protein, glucose, creatinine, phosphate, bicarbonate, blood, calcium): at 4 weeks and 12 weeks from Baseline and every 12 weeks thereafter to Week 96

Subjects enrolled to Group 2 will have the following monitoring:

- DEXA: every 48 weeks from Baseline to Week 96 (3 scans)
- Serum bone chemistry (i.e., calcium, phosphorus, vitamin D levels (25-hydroxy and 1,25 dihydroxyvitamin), PTH, osteocalcin, bone-specific alkaline phosphatase, N and C telopeptides): every 48 weeks from Baseline to Week 96
- Serum renal chemistry and urinalysis according local standards of care

Product, Dose, and
Mode of
Administration:

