300mg oral Tenofovir disoproxil fumarate (Tenofovir DF), which is equivalent to 245mg Tenofovir disoproxil, following enhanced patient monitoring protocol for bone and renal biomarkers

Reference Therapy,
Dose, and Mode of
Administration:

300mg oral Tenofovir DF following local standards of care for patient monitoring for renal biomarkers

Criteria for Evaluation:

Safety:

The primary safety endpoint is the indication of a cumulative incidence of a $\geq 4\%$ decrease from Baseline BMD of the spine or whole body through Week 96. Secondary endpoints include bone and renal AEs. Bone AEs may include reports of bone pain or fractures. Renal AEs may include reductions in creatinine clearance, and clinical and laboratory evidence of Grade 3 or greater renal tubulopathy or toxicity (e.g. proximal renal tubulopathy, Fanconi syndrome).

Bone and renal AEs, concomitant medications (including dietary supplements) and specified clinical laboratory tests will be collected each time subjects from Group 1 or Group 2 return for scheduled monitoring by the study site over a 96 week period.

Efficacy:

An efficacy analysis will be conducted after the last assigned subject reaches Week 96. The analysis will evaluate the difference in the proportion of subjects (Group 1 and 2 data will be pooled, as subjects have exposure to a single mode of therapy) achieving a composite endpoint of HBV DNA < 400 copies/mL and ALT normal at Week 96.

Pharmacokinetics: Not applicable

Statistical Methods:

The primary safety analysis will be performed after the last subject reaches Week 96 on Tenofovir DF treatment among both monitoring groups. The primary analysis will evaluate quantitative reductions in spine or whole body BMD compared to baseline assessments through DEXA scanning. A key secondary study objective is to assess within-group and between-group differences in renal biomarker changes (e.g., creatinine clearance using the Schwartz formula, glucosuria, proteinuria) suggestive of renal toxicity. To evaluate the time to detection of renal or bone AEs among the assigned monitoring groups, estimations of incidence rates (events over person time on Tenofovir DF) and time to event analysis will be determined. The evaluation of other clinically relevant endpoints such as sustained virologic response, serologic status, and development of Tenofovir DF resistance will also be assessed as secondary study outcomes for each monitoring group and as a combined cohort.

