Screening measures for Monitoring Groups 1 and 2 will include determining a subject's eligibility into the study with the following criteria: current age, documentation of chronic HBV infection, prior Tenofovir DF exposure, weight, laboratory assessments, ability to swallow solid tablets, subject's ability to adhere to treatment regimen, obtaining written informed consent from subject's parent or legal guardian or obtain informed assent from the subject

Baseline measures for Monitoring Groups 1 and 2 will include laboratory assessments for HBV DNA, HBV serology, HCV, HDV, and HIV polymerase chain reaction (PCR) testing, HBV genotyping, serum renal and bone chemistries, liver function, hematology, urinalysis. DEXA imaging, a physical exam (including pregnancy testing for females), current concomitant medications and any reported prior bone and renal AEs, will also be collected.

FREQUENCY OF STUDY PROCEDURES ([Appendix 2](#)):

Subjects enrolled to either Group 1 or 2 will have the following measures assessed:

- HBV DNA: every 12 weeks
- HBV serology: every 24 weeks
- Liver chemistry (i.e., alanine aminotransferase (ALT), alkaline phosphatase (ALP), aspartate aminotransferase (AST), total and direct bilirubin, total protein, albumin, gamma glutamyl transpeptidase (GGT), lactate dehydrogenase (LDH), creatine kinase (CK) every 24 weeks
- Hematology (i.e., complete blood count with differential and platelets, PT/INR): every 24 weeks
- Physical Examination and Drug Dispensing: every 12 weeks
- Documentation of bone or renal AEs since the subject's last visit
- Documentation of medical management in the event of bone or renal AEs

Subjects enrolled to Group 1 will have the following additional monitoring;

- DEXA: every 24 weeks from Baseline to Week 96 (5 scans)
- Serum bone chemistry (i.e., calcium, phosphorus, vitamin D levels (25-hydroxy and 1, 25 dihydroxyvitamin), parathyroid hormone (PTH), osteocalcin, bone-specific alkaline phosphatase, N and C telopeptides): every 24 weeks
- Serum renal chemistry (i.e., glucose, creatinine, calculated creatinine clearance, magnesium, bicarbonate, chloride, potassium, sodium): at 4 weeks and 12 weeks from Baseline and every 12 weeks thereafter, according to SmPC
- Urinalysis (i.e., protein, glucose, creatinine, phosphate, bicarbonate, blood, calcium): at 4 weeks and 12 weeks from Baseline and every 12 weeks thereafter

Subjects enrolled to Group 2 will have the following monitoring:

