Appendix 2. Study Procedures Table

Study Procedures	Study Week												
	Screening	Baseline	4	12	24	36	48	60	72	84	96	30d Follow-Up	
Written Informed Consent	x												
Medical History	x												
HBV DNA		x		x	x	x	x	x	x	x	x		
HBV serology	x	x			x		x		x		x		
HCV, HDV, HIV testing		x											
HBV genotype		x											
DEXA, Group 1		x			x		x		x			x	
DEXA, Group 2		x					x					x	
Serum bone chemistry, Group 1		x			x		x		x			x	
Serum bone chemistry, Group 2		x					x					x	
Serum renal chemistry, Group 1	x	x	x	x	x	x	x	x	x	x	x	x	
Serum renal chemistry, Group 2*	x	x										x	
Liver chemistry	x	x			x		x		x			x	
Hematology		x			x		x		x			x	
Urinalysis, Group 1 (see * for Group 2)	x	x	x	x	x	x	x	x	x	x	x	x	
Complete physical examination	x	x		x	x	x	x	x	x	x	x	x	
Changes in medical status or symptoms, Group 1 (see † for Group 2)		x	x										
Drug dispensed and accountability/Concomitant medications		x	x	x	x	x	x	x	x	x	x	x	
Assess for AE, including renal and bone events (see † for Group 2)		x	x	x	x	x	x	x	x	x	x	x	x
Pregnancy test	x	x		x	x	x	x	x	x	x	x	x	

[figure not shown]
* Group 2 will follow local standard of care for renal monitoring, which may include the Tenofovir DF SmPC recommended screening intervals

† Group 2 subjects may have changes in medical status or symptoms and new AE assessed upon return for renal monitoring, as per standard of care and within the 12 week intervals of scheduled physical examinations

Definitions:

HBV serology	HBeAg, HBsAg, anti-Hbe, anti-HBs
Serum bone chemistry	calcium, phosphorus, 25-hydroxy and 1, 25 dihydroxyvitamin, PTH, osteocalcin, bone alkaline phosphatase, N and C telopeptides
Serum renal chemistry	glucose, creatinine, creatinine clearance (calculated), magnesium, bicarbonate, chloride, potassium, sodium
Liver chemistry	alanine aminotransferase (ALT), alkaline aminophosphatase (ALP), aspartate aminotransferase (AST), total and direct bilirubin, total protein, albumin, gamma glutamyl transpeptide (GGT), LDH, CK
Hematology	PT/INR, complete blood count (CBC) with differential, platelets
Urinalysis	glucose, protein, creatinine, phosphate, bicarbonate, blood, calcium
Complete physical exam	includes vital signs, body weight and height

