7.2. Laboratory Evaluations

Selected laboratory data (using conventional units) will be summarized by the observed data and change over time. Missing laboratory results for safety summaries will not be imputed. In all cases for laboratory evaluations, no inferential statistics will be computed.

Glomerular filtration rate (estimated creatinine clearance) will be calculated via statistical programming at each visit

(a) using Schwartz formula for subjects ages 12–18 years (ie, 12 to < 19) as follows:

$$\text{Schwartz formula (mL/min/1.73 m}^2\text{)} = k \times L/\text{Scr}$$

k is a proportionality constant,

k=0.55 for adolescent females 12-18 years old; and

k=0.70 for adolescent males 12-18 years old

L is height in centimeters (cm); and

Scr is serum creatinine (mg/dL)

(b) using Cockcroft-Gault equation for age ≥ 12 years as follows:

$$\frac{(140 - \text{age in years}) (\text{body weight [kg]})}{(72) (\text{serum creatinine [mg/dl]})}$$

[Note: multiply estimated rate by 0.85 for women; use actual body weight]

Creatinine clearance (CLcr) summaries will be provided by Schwartz and Cockcroft-Gault separately.

Summaries and data listings will use the Safety Analysis Set. For subjects who discontinue prior to the final week for the given analysis, all on-treatment laboratory data collected on or before the date of last dose + 7 days will be included in tabular summaries. Laboratory data prior to the first dose date of TDF will be included in data listings.

Summaries of laboratory data will be provided for the safety analysis set. No inferential statistics will be generated.

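### Urine creatinine is collected at 11 scheduled Group 1 visits but never used as a denominator, so any numeric urine summary would be an unindexed, dilution-dependent concentration

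*SAP*

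**What the plan says.** The Protocol synopsis (Statistical Methods) makes it a key secondary objective to assess within-group and between-group "differences in renal biomarker changes (e.g., creatinine clearance using the Schwartz formula, glucosuria, proteinuria) suggestive of renal toxicity". Under Criteria for Evaluation it names proximal tubulopathy and Fanconi syndrome among the renal events of interest. Protocol 1.4 adds that a bone effect of the drug may show as increased calcium excretion.

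For Group 1, Protocol 3.2 specifies "Urinalysis (i.e., protein, glucose, creatinine, phosphate, bicarbonate, blood, calcium): at 4 weeks and 12 weeks from Baseline and every 12 weeks thereafter". Protocol Appendix 2 also marks Screening and Baseline. The samples are fasting.

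The SAP handles these results in four places:

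- **7.2 (scope):** "Selected laboratory data (using conventional units) will be summarized by the observed data and change over time". The only derived renal quantity is creatinine clearance from serum creatinine, by Schwartz and by Cockcroft-Gault.
- **7.2.1 (numeric summaries):** "Descriptive statistics (sample size, mean, standard deviation, median, Q1, Q3, minimum and maximum) will be provided by monitoring group for each laboratory test", as baseline, value and change by window.
- **7.2.2 and Appendix 2 (grading):** urine protein and glucose are graded by dipstick. Grades also exist for blood (dipstick and quantitative) and for 24-hour protein, but no 24-hour collection is scheduled. Urine phosphate, calcium and creatinine have no grade.
- **Appendix 3 (outputs):** Tables 21.1 to 21.3.3 cover calcium, phosphorus, creatinine and the two clearance estimates. No table title names a urine analyte or a ratio. Listings 17.1.1 and 17.1.2 show renal laboratory results, with columns not specified.

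**The concern.** Urine creatinine is the natural index for the other urine analytes: dividing by it removes most of the effect of how dilute the sample is. The plan collects it beside phosphate, calcium and protein and then treats it as one more test. A urine phosphate or calcium concentration from a sample that is not a timed collection mixes excretion with hydration, so it measures tubular loss or calcium excretion poorly.

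What is at stake is modest but bears on the trial's own targets. Graded renal events are expected to be few: Protocol 1.2.3.1 reports that, in the previous adolescent trial, no subject had a confirmed serum phosphorus below 2 mg/dL by Week 72. In a study that stopped at 30 subjects, continuous and dilution-corrected measures would describe renal tubular handling better than dipstick grades or raw concentrations, and they need no new samples.

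**Working it through.** The plan states no figure on this point, so there is none to reproduce. The check counts the visits at which each index can be formed, then shows what dilution does to each measure.

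**1. Where the indices can be formed**

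The ratios need urine analytes only. Fractional phosphate excretion also needs serum creatinine (renal panel) and serum phosphorus. Serum phosphorus is in the bone panel: "Serum bone chemistry (i.e., calcium, phosphorus, vitamin D levels".

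| Measurement | Group 1 | Group 2 |
|---|---|---|
| Urinalysis per protocol | Screening, Baseline, Weeks 4, 12, 24, 36, 48, 60, 72, 84, 96 (11; 9 on treatment) | Screening, Baseline, Week 96 (Protocol 6.2.1, 6.3.2, 6.4.6); otherwise local care |
| Serum phosphorus | Baseline, Weeks 24, 48, 72, 96 (5) | Baseline, Weeks 48, 96 (3) |
| Urine/creatinine ratios possible | 11 of 11 | 3 visits |
| Fractional phosphate excretion possible | 5 of 11 (4 of 9 on treatment) | Baseline, Week 96 |

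This follows the schedule tables, which mark no bone chemistry at Screening, although SAP 3.8.2 remarks that bone markers are also taken then.

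**2. Formulas**

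- Ratio = urine analyte / urine creatinine.
- Fractional phosphate excretion (%) = 100 × (urine P × serum creatinine) / (serum P × urine creatinine).

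**3. Dilution with excretion held fixed**

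Assumed values, none from the documents: urine phosphate 60, urine creatinine 100, serum phosphorus 4.0, serum creatinine 0.6 mg/dL. Both urine values are divided by the dilution factor d.

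| d | Raw urine phosphate (mg/dL) | Phosphate/creatinine | Fractional excretion |
|---|---|---|---|
| 0.5 | 120 | 0.60 | 9.0% |
| 1 | 60 | 0.60 | 9.0% |
| 2 | 30 | 0.60 | 9.0% |
| 3 | 20 | 0.60 | 9.0% |

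If phosphate loss doubles in urine twice as dilute, the raw value is 2 × 60 / 2 = 60, unchanged. The ratio becomes 60/50 = 1.20, and fractional excretion 100 × (60 × 0.6)/(4.0 × 50) = 18%.

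**4. Noise added by dilution**

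On the log scale, with dilution independent of excretion, the variance of the raw concentration relative to the ratio is [ln(1 + CVb²) + ln(1 + CVd²)] / ln(1 + CVb²). Here CVb is the biological CV and CVd the dilution CV. Both ranges are assumed.

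| CVd | CVb = 30% | CVb = 50% |
|---|---|---|
| 30% | 2.00 | 1.39 |
| 50% | 3.59 | 2.00 |
| 70% | 5.63 | 2.79 |

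The raw concentration thus has about 1.4 to 5.6 times the variance of the ratio.

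**5. A case in which the serum values also move**

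Assumed: urine phosphate 60 at both visits, urine creatinine 120 then 60, serum phosphorus 4.2 then 3.6, serum creatinine 0.60 then 0.65 mg/dL.

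- First visit: 100 × 60 × 0.60/(4.2 × 120) = 7.1%.
- Second visit: 100 × 60 × 0.65/(3.6 × 60) = 18.1%.
- The rise is 2.53-fold. Of this, 120/60 = 2 comes from urine creatinine, and (0.65/0.60) × (4.2/3.6) = 1.26 from the serum values.

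**The case against.** **Nothing promised is missing.** The protocol's renal biomarkers are given as examples: Schwartz clearance, glucosuria and proteinuria. The SAP derives the first and grades the other two. It also plans phosphorus and creatinine tables, a renal abnormalities table (24) and renal listings. No objective or endpoint names a urine ratio or fractional excretion. This stands: the point is an improvement, not a departure from the protocol.

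**Raw urine tables may not exist.** A reader might infer from 7.2.1 that the SAP tabulates raw urine concentrations. The documents do not establish this, because 7.2 limits summaries to selected data and Appendix 3 lists no numeric urine table. This also stands. What can be said is that any numeric urine summary would be unindexed, and that whether one is planned is unclear.

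**The plan would not necessarily miss phosphate loss.** A reader might infer that it would. In step 5, however, serum phosphorus falls by 14% and serum creatinine rises by 8%. Read as serum tables, 21.2 and 21.3.1 would show both. That serum phosphorus of 3.6 mg/dL is above the Grade 1 band for ages 1 to 14 (3.0 to 3.5) affects grading, not the change tables. Such illustrations pair loss with a dilution that exactly cancels it. They show that masking is possible, not how often it occurs.

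**The results may not be quantitative.** The documents speak of urinalysis, give no reporting units for the urine analytes, and do not describe the sample beyond fasting. This stands and makes the fix conditional.

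**Little depends on it.** Group 1 has 15 subjects, two subjects in the whole study completed 96 weeks, SAP 7.2 excludes inference for laboratory data, and SAP 2.1 says the study cannot inform the choice of monitoring frequency. This limits the gain without removing it, since SAP 2.1 turns to describing available exposure and the indices do that better than raw values.

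**Conclusion.** The point holds as a low-severity improvement. Urine creatinine is collected at all 11 scheduled Group 1 urinalysis visits, and no visible part of the protocol, SAP text or output list uses it as a denominator. The SAP's laboratory sections contain no blacked-out text that could hold such a definition.

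Under the assumed values, dilution alone moves raw urine phosphate six-fold (120 to 20 mg/dL) while the ratio and fractional excretion do not change. Under the assumed CVs, the raw value has 1.4 to 5.6 times the variance of the ratio. These figures rest on dilution acting equally on analyte and creatinine, stable creatinine output, and quantitative laboratory results; the documents confirm none of the three.

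A reader might also infer that the indices would rescue the comparison of the two monitoring schedules. They would not. Group 2 has protocol urinalysis only at Screening, Baseline and Week 96, and has serum phosphorus but no protocol urinalysis at Week 48. On-treatment indices would come almost entirely from Group 1.

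**What to change.** - **Scope.** State in SAP 7.2 whether numeric urine results are among the selected data, and make 7.2, 7.2.1 and Appendix 3 agree.
- **Ratios.** Where the laboratory reports quantitative values, derive urine phosphate/creatinine and calcium/creatinine at every visit with urinalysis. Add protein/creatinine only if protein is quantitative.
- **Fractional phosphate excretion.** Derive it with the formula above at visits with same-visit serum phosphorus. For Group 1 these are Baseline and Weeks 24, 48, 72 and 96; for Group 2, Baseline and Week 96.
- **Pairing.** Form each index from same-visit samples before window selection. SAP Tables 3-1 and 3-2 give general laboratory data and bone markers different windows, so matching by window could pair samples from different dates.
- **Output.** Add descriptive tables of baseline and change beside Table 21.2, mainly for Group 1, and keep the dipstick grades.

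The cost is a query to the laboratory about units and a little programming. No new samples, tests of significance or changes in patient care are needed. The downside is a few more descriptive tables, with few Group 2 values and few late visits.

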7.2.2. Graded Laboratory Values

The criteria specified in the study protocol will be used to grade laboratory results as Grade 0, mild (Grade 1), moderate (Grade 2), severe (Grade 3) or potentially life threatening (Grade 4). Grade 0 includes all values that do not meet criteria for an abnormality of at least Grade 1. Some laboratory tests have criteria for both increased and decreased levels; analyses for each direction (i.e., increased, decreased) will be presented separately. Grading of laboratory abnormalities for analysis purposes will be performed by the central laboratory.

Laboratory abnormalities may be reported as an AE, and the clinical grading of an event may be different from the quantitative grading depending on the clinical status and underlying conditions.

7.2.2.1. Treatment-Emergent Laboratory Abnormalities

Treatment-emergent laboratory abnormalities are defined as values that increase at least one toxicity grade from baseline at any time post-baseline up to and including the date of last dose of TDF plus 30 days. If the relevant baseline laboratory data are missing, then any abnormality of at least Grade 1 will be considered treatment emergent.

Treatment-emergent laboratory abnormalities and Grade 3 or 4 treatment-emergent laboratory abnormalities by monitoring group and overall will be summarized based on the date of the abnormality. Abnormalities that occur prior to the first dose date of TDF or during follow-up will be included only in data listings.

7.2.2.2. Treatment-Emergent Marked Laboratory Abnormalities

Treatment-emergent marked laboratory abnormalities are defined as values that worsen from baseline by at least 3 grades at any post-baseline, on-treatment value. On-treatment values include those up to and including the date of the last dose of TDF plus 30 days. If the relevant baseline laboratory data are missing, then any Grade 3 or 4 on-treatment values will be considered treatment-emergent marked abnormalities.

7.2.2.3. Summaries of Laboratory Abnormalities

The following summaries (number and percentage of subjects) of laboratory abnormalities will be provided by monitoring group (subjects categorized according to most severe abnormality grade), where applicable:

- Treatment-emergent laboratory abnormalities
- Treatment-emergent marked laboratory abnormalities

For all summaries of laboratory abnormalities, the denominator is the number of subjects with non-missing post-baseline values in the given study period. A listing of treatment-emergent Grade 3 or Grade 4 laboratory abnormalities will be provided.

Incidence of ALT flare and post-treatment exacerbation of hepatitis is defined as follows:

- Serum ALT $> 2 \times$ study BL and $> 10 \times$ ULN, with or without associated symptoms

OR

- Confirmed ALT elevation (defined as 1-grade shift [ie, increase] or $2 \times$ previous value) with confirmed changes outside of the normal range in other laboratory parameters suggestive of worsening hepatic function (total bilirubin ≥ 2 mg/dL above study BL, abnormal prothrombin time ≥ 2 seconds over BL or international normalized ratio [INR] ≥ 0.5 over BL, abnormal serum albumin ≥ 1 g/dL below BL or elevated serum lactate levels [if available], defined as $2 \times$ ULN).

Summaries (number and percentage of subjects) of treatment-emergent, on-treatment laboratory abnormalities will be provided by monitoring group and overall, with the following modifications for the creatinine summaries:

Confirmed (defined as 2 consecutive visits) increase in serum creatinine of 0.3 mg/dL above BL

Confirmed (defined as 2 consecutive visits) increase in serum creatinine of 0.5 mg/dL above BL.

A confirmed laboratory results is defined as either being present at 2 consecutive visits or at the last visit. If the first of 2 consecutive results is on-treatment and the second is off-treatment, then the result is considered confirmed.

For all summaries of laboratory abnormalities, the denominator is the number of subjects in the Safety Analysis Set.

Hepatic flares will be summarized by monitoring group and overall.

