8.6.3. Laboratory Evaluations

Selected laboratory data (using conventional units) will be summarized using only observed data. Data and change from baseline at all scheduled time points will be summarized.

Selected laboratory data (using conventional units) will be summarized by the observed data and by the change from baseline across time.

Graded laboratory abnormalities will be defined using the grading scheme defined in [Appendix 4](#). Grading of laboratory abnormalities for analysis purposes will be performed by the central laboratory.

Incidence of treatment-emergent laboratory abnormalities, defined as values that increase at least one toxicity grade from baseline at any time post baseline, will be summarized by monitoring group. If baseline data are missing, then any graded abnormality (i.e., at least a Grade 1) will be considered treatment-emergent.

Laboratory abnormalities that occur before the first dose of Tenofovir DF or after the last dose of Tenofovir DF plus 30 days will be included in a data listing.

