3.9. Handling Missing Data in Evaluation of Efficacy

3.9.1. Missing = Excluded Analysis

The primary method of handling missing data in evaluation of efficacy is the missing = excluded (M = E) approach. Due to the ad-hoc nature visits and tests within study group 2, M=E is preferred.

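### SAP 7.2.2.3 gives two incompatible denominators for all laboratory abnormality summaries and leaves the rule for a confirmed creatinine rise unclear

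*SAP*

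**What the plan says.** **Denominator.** SAP 7.2.2.3 first lists the summaries of treatment-emergent and marked abnormalities and states: "For all summaries of laboratory abnormalities, the denominator is the number of subjects with non-missing post-baseline values in the given study period". After the paragraphs on ALT flare, creatinine and confirmation it states: "For all summaries of laboratory abnormalities, the denominator is the number of subjects in the Safety Analysis Set". Neither sentence names an exception or a table.

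**Confirmation.** The creatinine lines in the same section read "Confirmed (defined as 2 consecutive visits) increase in serum creatinine of 0.3 mg/dL above BL", with a second line for 0.5 mg/dL. The sentence that follows them reads "A confirmed laboratory results is defined as either being present at 2 consecutive visits or at the last visit".

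**Testing schedule.** In the protocol's Appendix 2, the row "Serum renal chemistry, Group 2" has one post-baseline mark, which the matching table in SAP Appendix 1 places at Week 96. Otherwise Group 2 follows local care for renal chemistry and urinalysis; protocol 6.4.6 adds a Week 96 urinalysis with no group restriction. SAP 2.1 reports that only two patients completed 96 weeks, and SAP 1.4 that 15 were enrolled per group.

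**BMD.** Protocol 8.6.4 compares the groups on BMD loss of at least 4%, using 95% confidence intervals. SAP 7.3 gives by-group summaries without inference. SAP 7.8 opens by saying that no protocol-specified safety analysis was altered.

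**The concern.** Two programmers could each follow 7.2.2.3 faithfully and print different percentages in Tables 23.1 to 23.4 and 24. The difference is not neutral here, because test frequency is what was randomized. A rule that treats no test as a normal result can make the less-tested group look cleaner. Documenting renal and bone laboratory abnormalities is a stated secondary objective, so these tables are substantive output even in a descriptive report.

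The confirmation wording adds a second fork. A subject with one post-baseline creatinine value can never be confirmed under a two-consecutive-visit rule, yet needs only one high value under the rule that also accepts the last visit.

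**Working it through.** **1. Scheduled post-baseline tests** (protocol 3.2, 6.4 and Appendix 2; SAP Appendix 1)

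| Test | Group 1 | Group 2 |
|---|---|---|
| Renal chemistry | 9 (Weeks 4, 12, 24, 36, 48, 60, 72, 84, 96) | 1 (Week 96) plus local care |
| Urinalysis | 9 (same weeks) | 1 (Week 96, by 6.4.6) plus local care |
| Bone chemistry | 4 (Weeks 24, 48, 72, 96) | 2 (Weeks 48, 96) |
| Liver chemistry, hematology | 4 | 4 |
| DEXA | 4 | 2 |

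The DEXA counts agree with the protocol's own totals of 5 and 3 scans, baseline included.

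**2. Denominator.** With x abnormal subjects, m tested and 15 in the group, the Safety Analysis Set rule prints x/15 and the non-missing rule prints x/m. The first equals the second multiplied by m/15. The documents do not give m, so these values are illustrative, with x = 1:

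| Tested (m) | Safety Analysis Set rule | Non-missing rule |
|---|---|---|
| 15 | 6.7% | 6.7% |
| 12 | 6.7% | 8.3% |
| 8 | 6.7% | 12.5% |
| 5 | 6.7% | 20.0% |

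Suppose 3 of 15 tested in Group 1 and 1 of 5 tested in Group 2 are abnormal. The rate among those tested is 20% in both. The Safety Analysis Set rule prints 20% against 1/15 = 6.7%.

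**3. What the non-missing rule leaves.** Assume a 2% chance of an abnormal result per panel (range 1% to 5%), independent panels and full follow-up. The chance of at least one abnormal result is 1 − (1 − q)^k:
- k = 9: 1 − 0.98^9 = 16.6% (8.6% to 37.0%)
- k = 1: 2% (1% to 5%)

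More panels give more chances, whichever denominator is used.

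**4. Confirmed creatinine rise.** Same assumptions, scheduled panels only. Let s0 be the probability of no consecutive pair so far with the latest value normal, s1 the same with the latest value high, and d the probability that a pair has occurred. Start at s0 = 1 − q, s1 = q, d = 0. At each further panel the new s0 is (s0 + s1)(1 − q), the new s1 is s0·q, and d grows by s1·q, using the old values. The two-consecutive rule gives d; adding the last visit gives d + s1.

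| q | Rule | 9 panels | 1 panel |
|---|---|---|---|
| 1% | two consecutive | 0.08% | 0% |
| 1% | or last visit | 1.07% | 1% |
| 2% | two consecutive | 0.31% | 0% |
| 2% | or last visit | 2.27% | 2% |
| 5% | two consecutive | 1.90% | 0% |
| 5% | or last visit | 6.59% | 5% |

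At 2% and 15 subjects, the Group 1 expectation is 0.0031 × 15 = 0.05 of a subject under one rule and 0.0227 × 15 = 0.34 under the other.

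**5. BMD loss of at least 4%.** Assume the 5.8% in protocol 1.4 is cumulative over scans at Weeks 24, 48 and 72, with the same true risk in both groups and follow-up to Week 96. If crossings are fully transient, the rate per scan is 1 − (1 − 0.058)^(1/3) = 1.97%. Four scans then give 7.66% and two give 3.91%, a gap of 3.75 points (0.0375 × 15 = 0.56 of a subject). If crossings persist, the gap is 0.

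**The case against.** The strongest reply is that placement settles the matter: the first denominator follows the graded and marked summaries (Tables 23.1 to 23.4), and the second follows the creatinine and flare items (Table 24). That may be what was meant, but each sentence claims all summaries and the text never divides them.

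For confirmation the placement argument is better. The SAP introduces the creatinine lines as modifications, so two consecutive visits may be specific to creatinine and the broader sentence may serve the ALT flare definition. I therefore call this an ambiguity, not a plain contradiction. It still needs settling, because the broader sentence follows at once and makes no exception.

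A reader might infer that the Safety Analysis Set denominator breaches the documents' own conventions. They do not support that. "Selected laboratory data (using conventional units) will be summarized using only observed data" (protocol 8.6.3) leads into values and changes at scheduled time points; "Missing laboratory results for safety summaries will not be imputed" (SAP 7.2) bars imputing results, and a larger denominator imputes no value; "Due to the ad-hoc nature visits and tests within study group 2, M=E is preferred" (SAP 3.9.1) is an efficacy rule. These favour the non-missing denominator only as a matter of consistency.

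A reader might also infer that Group 2 is bound to look safer by a calculable amount. The number tested is unknown. Local care may follow the labelled testing intervals, and protocol 6.4.6 provides renal tests at an early-discontinuation visit. If local tests were prompted by illness, the non-missing denominator could overstate Group 2. That objection stands and limits what the fix can claim.

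On BMD, SAP 2.1 and 7.3 already make the analysis descriptive, and Tables 26.2 and 27.2 show percent change by week with a category for −4% or lower and one for missing scans. Detection under each schedule is also part of the study question. A claim that the final report contains a biased BMD test is not supported.

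**Conclusion.** The denominator conflict is real, needs no assumption to establish, and should be settled before the tables are programmed. It can lower Group 2 percentages for renal, urine and bone tests, but not through scheduling for liver or hematology tests. Its size cannot be given, because it rests on an unknown number tested. No confirmatory decision depends on it: SAP 7.2 computes no inferential statistics for laboratory data, and the groups have 15 subjects each.

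The confirmation rule is ambiguous. Its numerical effect is small under the assumed per-panel rates, but the choice decides whether a subject with a single value can count at all.

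The BMD part is minor: an inaccurate opening sentence in SAP 7.8, and two incidence tables that need a note on unequal scan numbers. The gap of 0 to 3.75 points depends wholly on how persistent crossings are, and on full follow-up, which few subjects had.

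**What to change.** 1. In SAP 7.2.2.3 delete the Safety Analysis Set denominator sentence. Use subjects with at least one non-missing post-baseline value for the test in question, and print that number by group in Tables 23.1 to 23.4 and 24.
2. Add a note to those tables: this denominator does not remove unequal ascertainment, since one group has more scheduled panels and local testing may be selective, so by-group rates are not a comparison of toxicity.
3. State which confirmation rule governs the creatinine lines, and print by group the number with at least two post-baseline creatinine values.
4. In SAP 7.8 say that the protocol 8.6.4 confidence-interval comparison of BMD loss of at least 4% is replaced by description. In Tables 26.1 and 27.1 note that scheduled post-baseline scans are 4 vs 2, and point to the same-week categories in Tables 26.2 and 27.2.

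I would not exclude Group 1's Week 24 and 72 scans to equalise the count. That discards data. If subjects stopped uniformly between Weeks 24 and 96 and had no early-discontinuation scan, (48 − 24)/(96 − 24) = one third would have no countable scan.

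The cost is SAP wording and table shells only. Denominators will vary by test and group, and percentages on few tested subjects will be unstable, which is why the counts must be shown.
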